2.2. Regulatory Status

The 3.0T Neonatal MRI investigational device is a pre-market magnetic resonance diagnostic device and its accessories and components are not yet cleared for commercial use (pre

market). In the United Kingdom (UK), the use of the device is subject to regulation by the Medicines and Healthcare Products Regulatory Agency (MHRA), in compliance with the Medical Devices Regulations of 2002 (transposition of European Medical Device Directive 93/42/EEC concerning medical devices, including Articles 3, 15, Annexes VIII and X).

The Expression MRI patient monitoring system (Invivo, Corp; Orlando, FL, USA) provided by the Sponsor for use in this have received CE mark for commercial use and are labelled for use in neonate and infant populations. All patient monitoring equipment will be used in accordance with its labelled indications, including meeting all conditions for MR scanning for MR Conditional devices.

2.3. Risk Category and Rationale

The MRI device used in this study uses static magnetic field strengths <4.0T, which are widely accepted to pose minimal risks to typical adults, children, and infants/neonates, as detailed in the US FDA Guidance *Criteria for Significant Risk Investigations of Magnetic Resonance Diagnostic Devices* and contemporary medical literature^{26,27}. During this study, subjects will encounter routine risks of transport outside of their regular care environment, which are considered mitigated to levels as low as reasonably practicable (ALARP) by design of the device and attendance of medical personnel throughout the subject's transport and study procedures. The 3.0T Neonatal MRI investigational device under study uses a 30T static magnetic field. The Sponsor's Risk Management procedures demonstrate that risks have been appropriately mitigated according to ISO 14971, in compliance with regulatory requirements set forth by the Medicines and Healthcare Products Regulatory Agency (MHRA), in compliance with the European Medical Device Directive 93/42/EEC.

2.3.1. MR Safe, Conditional, and Unsafe

Some medical devices placed into surgically or naturally formed cavities of the human body (implants) or other device or objects outside of the body may be allowed into the MR environment, however, MRI examinations may be contraindicated in patients with some types of passive or active implants that cannot be safely allowed in the MR environment. If these procedures and the site MR safety policy are followed, the risks associated with devices and objects within the MRI environment are considered to be no greater than routine clinical MRI scanning.

ASTM F2503 *Standard Practice for Marking Medical Devices and Other Items for Safety in the Magnetic Resonance Environment* provides terminology for classifying whether implants pose

potential hazards to patients in the MR environment that is recognized in the European Union and United States Food and Drug Administration (FDA), ^{[1],[2]} as follows:

Label	Description (typical use)
 or 	MR Safe
	MR Conditional
	MR Unsafe

Note: If the level of MR compatibility of the device in question is not known (not presented on the device label) or the device identity is not able to be determined, then an implanted device should be considered MR Unsafe for the purposes of this study, with the exception of dental devices/fillings, surgical clips, and surgical staples determined to be safe for MRI scanning by a physician investigator.

Special care should be taken in MRI with metal objects typically found on neonates and infants, such as umbilical cord clips and identification bands. The local site MR safety policy should be followed when determining if these devices are safe for MRI.

2.4. Device Classification and Rationale

In the United Kingdom (UK), the investigational 3.0T Neonatal MRI investigational device and its components and accessories used in this study are considered a Class IIa medical device per the European Medical Device Directive Annex IX, Rule 10. The Single-use Disposable Swaddle and its components and accessories are considered to be a Class I medical device per the European Medical Device Directive Annex IX, Rule 10.

In the UK, the Expression MRI patient monitoring systems (Invivo, Corp; Orlando, FL, USA) are considered Class IIa medical device per the European Medical Device Directive Annex IX, Rule 10.

2.5. Device Issuance and Replacement

2.5.1. Issuance and Installation

The Sponsor will ship to the study site and install the investigational 3.0T Neonatal MRI investigational device. The Sponsor will provide single-use disposable swaddles and

^[1] Establishing Safety and Compatibility of Passive Implants in the Magnetic Resonance (MR) Environment. US Food and Drug Administration (FDA). August 21, 2008, updated April 6 2011.

^[2] European Union (EU) Directive 2004/40/EC and 2008/46/EC

necessary hardware and software components and accessories for the investigational system.

If not already owned by the investigational site, the Sponsor may provide each site with Sponsor-owned Expression (Invivo Corp) patient monitoring systems labelled for use in neonate and infant populations according to MR Conditional labelling. Unique identifying information will be recorded for both Sponsor-provided and site-owned devices used in this study and a copy of this information will be stored in the Sponsor's *Device Accountability Log* stored in the Clinical History File (CHF).

2.5.2. Medicinal and Biologic Product Administration and Delay

No clinically indicated medical care will be additionally administered or delayed for any subject due to study participation. No medicinal agents (including sedatives), biologically active agents, or contrast agents not required for the subject's clinical care outside of this study will be administered for the purpose of this study, with the exception of routine sweet solutions ('sweeties') which may be used during the study period if prescribed by a physician.

Subjects that received sedatives or other clinically indicated medicinal or contrast agents as part of their regular clinical care may be included if there are no extensions of administration or delays to administration of clinically indicated medications (including treatments required to end sedation) as a result of study participation. Sedation may not be extended for the purpose of this study.

2.5.3. Future and Concurrent Use of Devices

This study is being conducted for engineering development and regulatory submission (including CE mark in the EU) of an investigational medical device and its components and accessories. After the device is CE marked, the device and/or its components may be used concurrently in other research activities in the EU under EC/IRB approved protocols, subject to, and required to adhere to, applicable local laws and regulations, and to the requirements of the Sponsor for device accountability. Any concurrent research activity will also be required to receive approval from the Sponsor and the institutional EC/IRB at the investigational site(s). This information may also be used for regulatory purposes in other countries outside of the EU. If the device is used in other countries, future and concurrent use will adhere to applicable laws and regulations.

2.5.4. Research Device Labelling

The device and related components will be labelled as an investigational device in accordance with local regulatory requirements in the UK. Labeling for investigational device(s) shall be provided by the Sponsor in a format approved by the Sponsor and consistent with local regulatory requirements at the investigational site.

2.5.5. Maintenance and Replacement

During this study, the Sponsor will be conducting engineering optimization and ensuring that the device(s) operate as intended, which may involve maintenance or replacement of hardware or software components of the device(s) and device accessories at the investigational site(s). To this end, Sponsor-authorized personnel may:

- a. Access device(s) in-person or remotely (such as through TVA/TIP or other secure remote connection) for quality control, trouble-shooting, training, real-time image optimization, to collect system configuration and system log files, or other purposes required for device maintenance, installation, de-installation, and/or system data collection;
- b. Conduct phantoms (simulated non-human) scans;
- c. Repair or replace the device or any of its components;

The Principal Investigator (PI) assumes responsibility for promptly reporting any device-related adverse events or product complaints observed by the PI or study staff to the Sponsors Clinical Affairs Project Manager (CAPM).

2.5.6. Security for Investigational Devices

1. **Single-use Disposable Swaddles:** Single-use disposable swaddles and non-disposable backboards will be uniquely and sequentially numbered and stored in a locked cabinet accessible to study staff. The investigational site will log the use and disposal of each swaddle ([Appendix B](#)). Swaddles are intended for use with the investigational device under this protocol, and swaddles may not be used outside of a Sponsor- and EC/IRB-approved study protocol. Each swaddle may be used only once, and may only be used on a single subject.
2. **Power Distribution Unit :** The Sponsor may lock the Power Distribution Unit (PDU) to secure the investigational device if changes are made to the device configuration requiring additional study staff training or maintenance.
3. **Host Computer:** The host computer will be accessible to authorized study staff, including the PI and trained scan operators, with a Sponsor-provided username and password.
4. **Security for the MR Environment** The investigational device will be housed in a secured environment that meets the Sponsor's engineering specifications for device installation. This area and the entrance to the scan room will be accessible only to the PI and trained study staff. The Principal Investigator assumes responsibility for meeting all investigational site and Sponsor requirements for securing the device.

2.6. Disposition of the Device/Product

When scanning under EC/IRB approved study protocols, the following actions will be conducted:

- a. The Sponsor will ensure that the device(s) and its components are dispositioned according to the contractual agreement reached between the investigational site and the Sponsor, in accordance with applicable local laws and regulations.
- b. The Investigator will ensure that used disposable components, such as used swaddles, will be handled according to the investigational site(s) standard procedures for disposal of biomedical waste.
- c. The Investigator will ensure that unused disposables and other non-disposable equipment provided by the Sponsor (including any Sponsor-provided Invivo Corp Expression patient monitor, hand-held metal detectors provided by the Sponsor, and the non-disposable backboard for the swaddles) are returned to the Sponsor.

3. OBJECTIVES OF RESEARCH STUDY

3.1. Hypothesis

There is no statistical hypothesis being tested in this study. Descriptive statistics will be used to provide summary evaluations of performance and safety data.

3.2. Justification

This study is being done in two parts to optimize and collect data from a new MRI device for use in neonates and infants, the 3.0T Neonatal MRI investigational device. The first part of this study is being conducted to demonstrate the feasibility and safety of attaining diagnostic quality images and data using the 3.0T Neonatal MRI investigational device in neonates and infants with various hardware and software configurations. The second part of this study is being conducted to collect images and associated data in neonates and infants from a fixed hardware and software configuration of the 3.0T Neonatal MRI investigational device in support of regulatory activities in the European Union (EU), including CE mark. MR system log files containing operating parameters relative to safety and performance calculations will be systematically collected throughout the study for all subjects. Summary performance and safety evaluations from both parts of the study may be disclosed to regulatory agencies as part of this study.

3.3. Study Objectives

3.3.1. Primary Objective(s)

To evaluate the safety and performance of the device by collection of images and associated data using the 3.0T Neonatal MRI investigational device that demonstrates the feasibility of use in clinical neonate and infant populations.

3.3.2. Secondary Objective(s)

To collect per-subject image quality, usability, workflow, and transport data.

To collect usability information for each device configuration (*pMR Procedure Document*)

To optimize device use and configurations, including software and hardware components functionality with MR accessories and performance factors.

3.3.3. Exploratory Objectives:

To record per-subject information, including clinical and demographic data.

To collect image data related to clinical follow-up conducted (if applicable) for engineering and device optimization purposes.

3.4. Study Endpoints

3.4.1. Primary endpoints

For both Phase 1 and Phase 2, primary endpoints will be recorded as:

- Collection of MR images and associated data per quotas (Section 5.1.1 - Quotas by Anatomic Region)

- Performance will be determined by summary proportions of images determined to be of evaluable or non-evaluable diagnostic quality
- Safety will be determined by summary rates of adverse events

3.4.2. Secondary endpoints

- MR image quality evaluation(s), per-phase as follows:
 - *Phase 1 and 2* (all subjects): Overall image quality rated on a 1-5 Likert scale
 - *Phase 1* Qualitative evaluation and optimization (Summary Report) provided by PI, as per applicable *MR Procedure Document*
 - *Phase 2*–Evaluations as described in the *MR Procedure Document*
- Per-subject Transport and swaddling times and data
- Per-subject workflow and transport information
- Per-subject formative and summative usability information (Appendix F– Example 3.0T Neonatal MR Investigational Device User Experience Questionnaire, Appendix G – Example of Single Use Disposable Swaddle System User Experience Questionnaire)
 - *Phase 1*– Collected as onsite Sponsor or study staff observations
(*may be completed by Sponsor staff trained on the study protocol and/or onsite study staff*)
 - *Phase 2*– Collected by onsite assessments by the scan operator
(*must be completed by trained site study staff*)
- Number and type (as determined by Sponsor engineering representative based on investigator device complaint reports) of device issues, as follows:
 - Technical Issues (caused by operator error)
 - Malfunctions (device did not perform as intended)

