6.3.4. Evaluations

Performance Evaluation

Image sets will be labelled according to subject identification number. Images will be evaluated as evaluable (diagnostic) or non-evaluable (non-diagnostic) by two evaluators, and then evaluable images will be read for image quality by a separate reader, as shown in [Figure 2](#).

[figure not shown]

Figure 2– Flowchart of performance evaluation. Determination of evaluable/non-evaluable for diagnostic purposes will be used as the primary performance measure. All secondary Image Quality Assessments will be descriptively summarized.

MR image datasets for each subject will be evaluated twice by two delegated radiologists serving as image evaluators (Evaluator 1 and Evaluator 2) as:

- Evaluable (Diagnostic Quality)⁶, or
- Non-evaluable (Non-Diagnostic quality)

The evaluations and printed name and signature of the image evaluator(s) will be recorded to an Evaluator CRF. In the event that the two evaluators (Evaluator 1 and Evaluator 2) disagree on whether an image is evaluable or non-evaluable, a third medically qualified reader (Reader 1) will arbitrate to provide an evaluable/non-evaluable decision, which will be recorded to the Reader CRF and treated as the final decision for the image set.

Image Quality Assessments

All evaluable images will be further examined by a single reader (Reader 1) that may be the PI or a qualified delegated radiologist for image quality on a 1-5 Likert Scale,⁷ as follows:

- Overall image quality

⁶ An image set may be considered of diagnostic quality if it contains images suitable for diagnosis (not all images views are typically required to be diagnostic based on specific scanning circumstances, so long as applicable views necessary for diagnosis are present)

⁷ Likert Scale of 1-5, where:

- 1 = Very Poor
- 2 = Poor
- 3 = Neutral
- 4 = Good
- 5 = Excellent

Note For image quality assessment, scores of 3, 4, or 5 will be considered diagnostic quality, and scores of 1 and 2 will be considered nondiagnostic quality.

- Image contrast
- Presence of artefacts
- Signal to noise ratio (SNR)
- Tissue contrast
- Fat/water homogeneity
- Additional Sponsor-Requested Assessments
 - CRF fields (10 blank “Assessment Title” lines with associated 1-5 Likert scales) will be provided on the CRF to accommodate Sponsor-requested elements that may be specified for each *MR Procedure Document*

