APPENDIX B EXAMPLE OF MR PROCEDURE DOCUMENT	
The Sponsor provided this MR Procedure document on _____ Date (DD/Mmm/YYYY)	
MR Procedure Document Version _____ Effective date (begin study procedures on or after): _____ Date (DD/Mmm/YYYY)	
Specific Instructions for procedures to be performed (attach additional pages, if necessary)	

Sample Document – Not for Study Use (Please use most current Sponsor provided document version)
	
Sponsor Requested Assessments of performance on a 5 Likert Scale (mark each assessment required)	
 Overall Image Quality (required for all subjects)	Other Assessments:
Other Engineering Performance Measures	 _____ (specify)
 Performance parameter _____ specify	 _____ (specify)
 Performance parameter _____ specify	 _____ (specify)
 Performance parameter _____ specify	 _____ (specify)
 Image contrast	 _____ (specify)
 Artefacts	 _____ (specify)
 Fat/water homogeneity	 _____ (specify)
 Signal-to-noise ratio	 _____ (specify)
 Reconstruction software performance	 _____ (specify)
 Signal-to-noise ratio	 _____ (specify)
 Reconstruction software performance	 _____ (specify)

Study Title: Development of a MR Scanner Capable of Being Sited in a Neonatal Intensive Care Unit

Study Number: 114-2014-GES-0035

Protocol: 7.0

GE Healthcare

Signature of Sponsor Engineering Representative	Date

Printed Name of Sponsor Engineering Representative	
Sample Document – Not for Study Use (Please use most current Sponsor provided document version)	

Signature of Clinical Affairs Project Manager	Date

Printed Name of Clinical Affairs Project Manager	

Signature of Principal Investigator or delegate	Date Received

Printed Name of Principal Investigator or delegate	

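### Overall image quality is an endpoint for all subjects, but section 6.3.4 has it scored only in sets already judged evaluable; at the planning rate about 18% of scanned sets would have no score.

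*Combined protocol and SAP*

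**What the plan says.** Three places define image quality as something measured on each subject.

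- Section 3.4.2, for Phases 1 and 2: "all subjects): Overall image quality rated on a 1-5 Likert scale".
- Section 3.3.2, secondary objective: "To collect per-subject image quality, usability, workflow, and transport data".
- Appendix B, the sample MR Procedure Document, where the box is already ticked: "Overall Image Quality (required for all subjects".

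Section 6.3.4 describes how the score is obtained. Two evaluators classify each set as evaluable or non-evaluable. If they disagree, "a third medically qualified reader (Reader 1) will arbitrate to provide an evaluable/non-evaluable decision". The opening paragraph then says that "evaluable images will be read for image quality by a separate reader", and the Image Quality Assessments paragraph repeats the restriction: "All evaluable images will be further examined by a single reader (Reader 1"). Table 3 in section 6.6 gives the quality ratings to the reader and not to the evaluators.

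A footnote to section 6.3.4 ties the scale to diagnostic status: "scores of 3, 4, or 5 will be considered diagnostic quality, and scores of 1 and 2 will be considered nondiagnostic quality". Section 6.2.1 carries the same rule. Section 8.1.2 plans descriptive summaries but names no denominator for this score, and section 8.3, on missing data, has no rule for a set without one.

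**The concern.** The endpoint covers all subjects, while the collection step covers only those whose images have passed the evaluability call. The missing scores are therefore not missing at random: a set is left out because its quality was poor, and quality is what the score measures. An average or a distribution over the scored sets describes images that passed. If it is read as describing all subjects, as the endpoint's definition invites, it will tend to flatter the device. Section 3.2 says that summary evaluations from both phases may go to regulators, so the label on that summary matters.

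The scale itself shows the gap. Grades 1 and 2 are set aside for non-diagnostic images, but sets judged non-diagnostic are removed before anyone grades them, which leaves those grades largely unused. Optimising the device is also a secondary objective, and poor sets carry information for that purpose.

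**Working it through.** **Inputs.** From section 8.1.1: 82% of images evaluable (a literature rate), 20% dropout, and a target of 30 + 5 = 35 evaluable sets. From section 5.1: at most 60 subjects enrolled. I assume one set per subject, since section 8.1.1 calls more than one exceptional, and dropout before scanning unless stated otherwise.

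**The plan's own figure.** 0.82N − (0.82N)(0.2) = 0.656N = 35, so N = 35/0.656 = 53.35. The plan states 53, so its figure reproduces. Strictly, 53 yields 53 × 0.656 = 34.8 sets and rounding up gives 54, but the ceiling of 60 covers the difference.

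**Unscored sets.** Write r for the evaluable rate. Scanned sets needed for 35 evaluable = 35/r; unscored = 35/r − 35; unscored share = 1 − r. Only the 82% row uses a rate stated in the plan. The 72.9% row is the lowest rate at which the ceiling still gives 35 evaluable sets: 60 × 0.80 = 48 scanned, and 35/48 = 0.729. The 95% and 70% rows are assumptions.

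| r | Scanned for 35 evaluable | Unscored | Share |
|---|---|---|---|
| 95% (assumed) | 36.8 | 1.8 | 5% |
| 82% (section 8.1.1) | 42.7 | 7.7 | 18% |
| 72.9% (35/48) | 48 | 13 | 27.1% |
| 70% (assumed) | 50.0 | 15.0 | 30% |

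The last row needs more than the 48 available. At 48 scanned, a rate of 70% gives 33.6 evaluable and 14.4 unscored.

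**At the ceiling of 60, r = 82%.** 48 × 0.82 = 39.4 scored and 48 × 0.18 = 8.6 unscored. With no dropout, 60 × 0.18 = 10.8 unscored.

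**Effect on the summary.** The true shift cannot be derived, because the plan gives no score distribution. Bounds follow only if scores obey the footnote cut-off, with evaluable sets at 3 to 5 and non-evaluable sets at 1 or 2. Let m_e and m_n be the mean scores of the two groups.

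- Mean over all scanned = r·m_e + (1 − r)·m_n, so the evaluable-only mean exceeds it by (1 − r)(m_e − m_n).
- Under the cut-off, m_e − m_n lies between 3 − 2 = 1 and 5 − 1 = 4.
- The excess is then 0.18 to 0.72 points at 82%, 0.05 to 0.20 at 95%, and 0.30 to 1.20 at 70%.
- As a percentage graded 3 or higher, under the same assumption: 100% of scored sets against r of all scanned sets, so 100% against 82% at the planning rate.

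**The case against.** The strongest reply is that the protocol leaves another route open. Section 6.2.1 lists overall image quality among the assessments an MR Procedure Document may request, Appendix B has it ticked for every subject, and the CRF has blank Likert lines at the scanning and post-scan stages. Section 6.3.4 never says that only evaluable sets are scored, and its Figure 2 is not reproduced in the text available. Table 3 shows who scores, not which sets. Taking the endpoint literally is also impossible, since subjects who drop out before scanning have no images.

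Part of this stands. Table 3 by itself does not establish the restriction; the two sentences in section 6.3.4 do. An MR Procedure Document could ask for the score, but no text asks for it in non-evaluable sets. At the reader stage, the extra assessments are listed under the same sentence that limits the reading to evaluable images. Scoring at the scanner would sit badly with Table 3's allocation to the reader. Reading the endpoint's population as merely meaning both phases does not fit Appendix B or the per-subject objective.

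On size, it is fair to say that 82% is a literature rate for images and not a rate for this device. A set may also pass without every view being diagnostic ("not all images views are typically required to be diagnostic based on specific scanning circumstances"), so the true rate could be higher; hence the range. The mean-shift bounds are conditional, and their extremes need every set at the end of its band.

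On harm, the study tests no hypothesis (section 3.1), the endpoint is secondary, and the success criterion in section 8.4 sets no score threshold. The proportion of non-evaluable sets is itself the primary performance measure (section 3.4.1), and section 5.1.2 keeps those sets in reported enrolment. If the cut-off held exactly, an unscored set would be known to be a 1 or a 2. These points limit the consequence; they do not make the definition and the procedure agree.

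**Conclusion.** The concern holds. As written, section 6.3.4 does not collect the endpoint that section 3.4.2 and Appendix B define, and the sets it leaves out are selected on the quality being measured. About 18% of scanned sets would be unscored at the planning rate, with a range of 5% to 30% for assumed evaluable rates of 95% to 70%. This rests on one set per subject and, for the counts at the ceiling, on dropout before scanning. The direction of the distortion, too favourable, is what one would expect; its size in score points cannot be derived without assuming the footnote cut-off. The matter should be corrected, but it does not threaten the primary performance endpoint.

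**What to change.** Preferred: amend section 6.3.4 so that Reader 1 gives the overall image-quality score to every acquired set, where possible without seeing the evaluators' decisions. Any arbitration call should be recorded before the score. Arbitrated sets cannot be fully blind, because the request shows that the evaluators disagreed, so flag them. In section 8.1.2, summarise overall quality over all scanned subjects first and evaluable sets second, and give the number unscored with the reason, such as no images acquired. State that the evaluator or arbiter call alone defines diagnostic quality, so that the Likert cut-off does not become a second definition.

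Alternative: if non-evaluable sets are not to be scored, restate section 3.4.2 and Appendix B as evaluable sets only, and print the number excluded beside every quality summary.

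Cost of the preferred change: about 8 to 9 extra reads at the planning rate (about 2 at 95% evaluable, 13 at 72.9%). Section 5.1.2 already has incomplete sets stored, and the reader is already assigned. It also needs small edits to the Reader CRF and section 6.3.4, and to Figure 2 if it shows the same routing. The reported scores will probably be less favourable. The alternative costs wording only.
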